#### **1.3.6 Reinfection following acute HCV infection**

The risk of reinfection is often cited as a reason for not offering treatment to current and former PWID, but few studies have evaluated the incidence of HCV reinfection following successful treatment in this context. The limited evidence would suggest that the reinfection rate is low. Of 111 subjects treated in the ATACH study, viral recurrence after treatment-induced suppression was observed in 19% (17/88) with 5 cases of reinfection (4.7 cases per 100 py; 95% CI 1.9, 11.2) (72). Ongoing IDU during follow up was reported by 38% of participants with treatment-induced virological suppression, with a higher reinfection rate in this subgroup (7.3 per 100 py [95% CI: 2.3, 22.6]). In the ATACH Recall study, 50 individuals from the original ATACH cohort were reassessed at a median duration of 7.2 years following primary infection with 37 (74%) having received treatment (SVR 24 70%) and 10 (20%) having demonstrated spontaneous clearance (73). Only 4 reinfections were identified (with 3 related to ongoing IDU) for an incidence rate of 1.8 per 100 py (95% CI: 0.7, 4.8). Importantly, significant changes were noted in injecting behaviour; 66% (33/50) had acquired HCV via IDU, but only 30% (15/50) reported ongoing use.

Two systematic reviews have examined the risk of reinfection in PWID after treatment-induced SVR, combining studies of acute and chronic HCV infection. In the first, the pooled estimate of reinfection from 5 prospective studies was 2.4 per 100 py (95% CI: 0.9, 6.1), rising to 6.4 per 100 py (95% CI: 2.5, 16.7) in those reporting ongoing IDU post SVR (74). The second systematic review and meta-analysis revealed similar findings with viral recurrence (late relapse or reinfection) in the “high risk” group (PWID, prisoners) estimated at 2.8 per 100 py (95% CI 2.06, 3.71) (75). Contrary to this, reinfection rates in predominantly young adult PWID who exhibited spontaneous clearance are higher, suggesting that this cohort may be at especial risk, though the number of subjects available for assessment was small (76-79).

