### **2.3 Secondary objective(s)**

- 1 To evaluate the proportion of participants with HCV RNA below the level of quantitation (TND or TDnq) at the end of treatment (ETR), 4 weeks after treatment completion (SVR4) and 24 weeks after treatment completion (SVR24);
- 2 To evaluate the proportion of participants with undetectable HCV RNA through 2 years post treatment;
- 3 To evaluate the levels of adherence, factors associated with suboptimal adherence including HIV status, and the impact of suboptimal adherence on therapeutic response;
- 4 To evaluate the impact of treatment on illicit drug use, injecting behaviour and sexual risk taking behaviour (behavioural survey) during treatment;
- 5 To evaluate safety and tolerability
- 6 To evaluate the change in HIV RNA and CD4 (on-treatment and end of treatment);
- 7 To evaluate the rate and risk factors for reinfection during and up to 2 years following treatment;
- 8 To evaluate the immunological factors associated with treatment induced clearance and reinfection
- 9 To evaluate patient interest and attitudes towards long acting parenteral hepatitis C therapy (Long-Acting Hepatitis C Therapy Questionnaire)

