#### Baseline visit (Week 0)

- Vital signs and physical examination
- HCV RNA (Local laboratory)
- LFTs, FBC and biochemistry
- Pregnancy test (females of child bearing potential only)
- Adverse Events
- Concomitant medication
- Abbreviated Behavioural questionnaire
- Long-Acting Hepatitis C Therapy Questionnaire\*
- Research specimen collection (EDTA plasma, whole blood & ACD Plasma/PBMCs)

\* The Long-Acting Hepatitis C Therapy Questionnaire aims to obtain participant interest and attitudes towards long-acting parenteral hepatitis C therapy. All currently enrolled participants will complete the Long-Acting Hepatitis C Therapy Questionnaire at their next scheduled visit.

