## **The Behavioral Questionnaire**

The study staff will assist participants to complete this questionnaire. The behavioural survey will collect information on the following:

- Demographics
- HIV and drug treatment history
- Drug and alcohol usage
- Injecting risk behaviours
- Sexual risk behaviours
- Treatment acceptance and willingness (prior to treatment commencement only)
- Attitudes and behaviours associated with HCV reinfection

An abbreviated behavioural questionnaire (follow-up) will be administered at subsequent time points during the study.

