- To evaluate the immunological factors associated with treatment induced clearance and reinfection;
- To evaluate patient interest and attitudes towards long acting parenteral hepatitis C therapy (Long-Acting Hepatitis C Therapy Questionnaire).

Hypothesis

Six weeks treatment with sofosbuvir/velpatasvir is non-inferior to twelve weeks treatment with sofosbuvir/velpastavir as assessed by sustained virological response at 12 weeks post treatment in the intention-to-treat population (SVR12).

Study design (Figure 1)

This is an open label multicentre study. The study consists of a screening phase, treatment phase and follow-up phase to evaluate treatment response and reinfection. Participants will be required to wait a minimum of four weeks from screening before commencing treatment to assess for spontaneous clearance. The maximum wait period allowed between screening and baseline is 12 weeks.

[figure not shown]

Figure 1: Study Schema

Sample size and power

The primary objective of this trial is to establish the non-inferiority of short duration treatment (6 weeks) to the standard duration treatment (12 weeks). Assuming an expected SVR of 90% in the control arm, 113 participants per arm will be required to give 80% chance that the two-sided confidence interval of the difference between regimens has a lower limit greater than -12%.

A total of 250 subjects enrolled and randomised will comprise the intention-to-treat (ITT) population and will form the study population for evaluation of the primary and secondary endpoints.

TYPE OF ANALYSIS

This document describes the primary statistical analysis for REACT study in accordance with protocol version 5.0.

Data Safety and Monitoring Board (DSMB) Analysis

This study has a DSMB to review the progress and safety of the study. The DSMB conducted an interim safety and adherence analysis when the first 50 participants had either reached post-treatment week 12 or dropped out of the study and then when a further 10 per arm reached 12 weeks post treatment. At the second review the DSMB recommended termination of the short arm of the study due to inferiority. At the stage of the DSMB recommendation, a total of 196 participants had been randomised, 192 had completed their randomised treatment, a further 4 were randomised to receive 6 weeks and extended to 12 weeks. Therefore, the primary analysis population will be based on 192 participants (99 in standard Arm, and 93 in shortened arm).

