Primary analysis: Post-treatment week 12

The analysis for the primary endpoint, SVR12, will be conducted after all participants have completed the post-treatment week 12 visit or prematurely discontinued from study. All the safety and efficacy data through to the post-treatment week 12 visit will be cleaned, finalised, and included for the analysis.

GENERAL CONSIDERATIONS FOR DATA ANALYSES

Statistical Methods

Analysis results will be presented using descriptive statistics. For categorical variables, the number (n) and percentage of participants in each category will be presented. For continuous variables, the number of participants (n), mean and standard deviation (SD), median, interquartile range (IQR, Q1-Q3), range (minimum, maximum) will be reported; for inclusion in the manuscript, an appropriate determination will be made depending on the variable, size and distribution of the population studied.

Statistical tests will be 2-sided and performed at the 5% significance level unless specified.

For all efficacy endpoints, means and proportions with two-sided 95% confidence intervals (CI) will be determined. For the analysis of categorical outcomes, Chi-squared tests or exact equivalents (for small numbers) will be used. For comparison of continuous measures, t tests or non-parametric equivalents will be used as appropriate for the observed data distribution. Changes in injecting behaviour between screening, end of treatment and post-treatment week 12 will be compared using the McNemar test (exact binomial probability).

Analysis Sets

Analysis sets define the subjects to be included in an analysis. The number of participants eligible for each analysis set will be provided. Participants who were excluded from each analysis set will be summarised, with reasons for exclusion.

Full Analysis Set (ITT population)

The FAS includes all enrolled participants who were randomised. This will be the analysis set used for the primary efficacy and safety endpoints. Following the DSMB recommendation to cease the study, the primary analysis population will be based on 192 participants (99 in standard Arm, and 93 in shortened arm).

Modified Full Analysis Set

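### The McNemar test for injecting behaviour takes screening as its pre-treatment point, 4 to 12 weeks before the first dose, and does not use the questionnaire collected at day 0

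*SAP*

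**What the plan says.** **Objective.** Protocol section 2.3, item 4, repeated in the SAP's secondary objectives: "To evaluate the impact of treatment on illicit drug use, injecting behaviour and sexual risk taking behaviour (behavioural survey) during treatment".

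**Test.** SAP, Statistical Methods: "Changes in injecting behaviour between screening, end of treatment and post-treatment week 12 will be compared using the McNemar test", in its exact binomial form. Day 0 is not among the three time points, and no other test of behaviour change is named.

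**Wait.** SAP, Study design: "Participants will be required to wait a minimum of four weeks from screening before commencing treatment to assess for spontaneous clearance", and "The maximum wait period allowed between screening and baseline is 12 weeks". Protocol section 4.2 sets the same limits.

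**Questionnaires.** In protocol section 6.1, screening uses the full study questionnaire. The Week 0 visit lists the "Abbreviated Behavioural questionnaire", and so do the end-of-treatment and post-treatment week 12 visits. Section 6.3 agrees: "An abbreviated behavioural questionnaire (follow-up) will be administered at subsequent time points during the study". The Schedules of Assessments mark a behavioural questionnaire at baseline in both arms.

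**Baseline convention.** The SAP's Analysis Windows section generally takes as baseline the latest available result at or before the first dose. The McNemar sentence departs from this without giving a reason.

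**Status.** SAP Table 12 lists the behavioural objective among additional pre-specified outcomes and marks it as outside the primary analysis.

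**The concern.** McNemar's test compares each participant with himself or herself at two visits, so whatever happens between those visits enters the result. If the first visit is screening, the result combines change over 4 to 12 untreated weeks with change on treatment and cannot separate them. Participants are enrolled because they acquired HCV recently, so some fall in risk behaviour before dosing, for reasons unrelated to the drug, is plausible. At stake is the reading of secondary objective 4: a fall completed before the first tablet could be presented as change over the treatment period. The measurement needed to avoid this is already scheduled, on the form that matches the later visits.

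**Working it through.** The plan gives no sample size, power or expected rate for the behavioural analysis, so there is no figure to reproduce.

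**1. Untreated share of the interval, in time**

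Inputs: wait w = 4 or 12 weeks (SAP, Study design); treatment t = 6 or 12 weeks (protocol section 5.1); follow-up of 12 weeks to the second contrast.

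Share to end of treatment = w / (w + t). Share to post-treatment week 12 = w / (w + t + 12).

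| Arm | Wait | To end of treatment | To post-treatment week 12 |
|---|---|---|---|
| 6 weeks | 4 | 4/10 = 40% | 4/22 = 18% |
| 6 weeks | 12 | 12/18 = 67% | 12/30 = 40% |
| 12 weeks | 4 | 4/16 = 25% | 4/28 = 14% |
| 12 weeks | 12 | 12/24 = 50% | 12/36 = 33% |

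With day 0 as the reference, w drops out and the pre-dose share is 0%. These are shares of calendar time. They would be shares of behaviour change only if behaviour moved at a constant rate unrelated to treatment, which the documents do not show.

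**2. What the exact test would do under assumed change rates**

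Let a be the proportion of participants who start injecting and s the proportion who stop. The number of discordant pairs n is Binomial(N, a + s). Given n, the number of stoppers b is Binomial(n, s/(a + s)). The test rejects when 2 × P[Binomial(n, ½) ≥ max(b, n − b)] ≤ 0.05. Summing over n and b gives the probability of a significant result.

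N is 192 pooled, or 93 and 99 by arm (SAP, Analysis Sets). The change rates are assumptions: a = 3% or 5%; s = a plus a net fall of 2, 5 or 10 percentage points; the whole net fall occurs before day 0. For the day-0 contrast, s = a.

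| Net fall during wait | From screening, N = 192 | From screening, N = 93–99 |
|---|---|---|
| 2 points | 8–11% | 4–5% |
| 5 points | 36–48% | 16–22% |
| 10 points | 86–93% | 51–66% |

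From day 0, with no net change on treatment, the probability is about 1–3% throughout. This shows the mechanism only; it does not estimate what happened in the trial.

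**3. Recall period**

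The SAP's Table 10 footnote defines recent injecting over 6 months and current injecting over the past month. Take 6 months as about 26 weeks. A 6-month answer at end of treatment reaches back 26 − 6 = 20 weeks before the first dose in the 6-week arm and 26 − 12 = 14 weeks in the 12-week arm. At post-treatment week 12 it still reaches back 26 − 18 = 8 and 26 − 24 = 2 weeks. A past-month answer at end of treatment falls within the treatment period in both arms. At day 0 it describes the month before dosing, whereas at screening it describes a month that ended at least 4 weeks before dosing. Moving the reference visit therefore works only with a short-recall item.

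**The case against.** **The SAP sentence does not attribute change to treatment.** It speaks only of changes between visits, and Table 12 places the behavioural objective outside the primary analysis. This stands: the attribution comes from objective 4. But no other test is given for that objective, so this rule is the one likely to be applied.

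**Screening values may be intended where nothing later exists.** The SAP lets its baseline table show screening values for pre-specified variables and for those recorded only at screening. That provision concerns the baseline table and does not explain passing over a day-0 form in a test of change. The questionnaire items are not in the documents, so equivalence between visits is an inference. It is a reasonable one, since the abbreviated form must supply the injecting data at the two later visits.

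**The bias may be small.** A reader might take the protocol's background figures as evidence of a steep fall: "66% (33/50) had acquired HCV via IDU, but only 30% (15/50) reported ongoing use". They are not a before-and-after comparison. The first is mode of acquisition; the second is ongoing use at reassessment, a median of 7.2 years after infection. Spread evenly, 36 points over 7.2 years is 5 points a year, or about 0.4 points in 4 weeks and 1.2 in 12, below the smallest scenario above. A steeper early fall is possible, but the documents do not show one. Nor is screening necessarily close to diagnosis: the first positive test may be up to 6 months old, so some change may already have occurred.

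**The arms are not biased against each other.** Because the time shares differ by arm, a reader might infer a distorted between-arm comparison. Randomisation takes place between weeks 5 and 6, after the wait, so the expected absolute pre-dose change is the same in both arms. Only the treated time added to it differs.

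**Day 0 does not isolate a treatment effect.** This also stands. No arm is untreated, so counselling, regression to the mean and secular trends can continue after day 0.

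**Conclusion.** The point holds as a choice of reference visit that does not match the objective. The two contrasts with screening include 4 to 12 weeks of untreated time: 25–67% of the interval to end of treatment and 14–40% of the interval to post-treatment week 12. Any behaviour change in that time is counted in the result. How much change that is cannot be determined from the documents, and the rejection probabilities above depend on assumed rates.

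A reader might go further and conclude that 25–67% of any reported change is spurious, or that screening is what prevents objective 4 from being answered. Neither is supported. The first treats time as behaviour change. The second overlooks that a single-group before-and-after comparison remains non-causal from day 0 as well. The contrast between end of treatment and post-treatment week 12 does not involve screening, and nothing here bears on SVR12 or the non-inferiority conclusion. This is an inexpensive correction to a secondary objective, worth making before the behavioural data are analysed.

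**What to change.** In the SAP's Statistical Methods:

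- Name baseline (day 0) as the pre-treatment reference for the McNemar comparisons with end of treatment and with post-treatment week 12.
- Specify past-month injecting items from the abbreviated form, and state the recall period.
- Report screening-to-day-0 change separately, labelled as change during the untreated wait.
- Keep the screening contrast as a labelled supplement, or for items asked only at screening.
- State that, without an untreated control, change from day 0 describes the treatment period and is not a causal effect.

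The cost is a few lines of SAP text and one additional tabulation; the day-0 questionnaire is already scheduled in both arms. The limitation is that items missing from the abbreviated form cannot be re-anchored, so the item lists of the two forms should be compared first.

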To assess HCV reinfection, among people with virological suppression, participants with HCV RNA recurrence (detectable HCV RNA following HCV virological suppression) will be identified. HCV RNA sequencing will be performed on the first available detectable HCV RNA sample and the first available detectable HCV RNA sample following HCV RNA recurrence. HCV reinfection will be defined by the detection of infection with an HCV strain which was distinct from the primary infecting strain based on previously defined genetic distance-based cut-offs for HCV reinfection and HCV viral relapse(72), patristic distance-based cut-offs and phylogenetic tree construction (86). Rates of HCV reinfection will be calculated using person-time of observation up to 48 months following the end of treatment. Modified intention-to-treat analyses will also be performed in which individuals with confirmed reinfection are removed from the efficacy analysis.

Immunological and virological assays will also be performed to assess the impact of HCV treatment on immune responses during treatment.

A final full statistical analysis plan will be written and signed off by the Protocol Steering Committee prior to final study data lock.

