MedDRA	Medical Dictionary for Regulatory Activities
MELD	Model for End-Stage Liver Disease
PT	preferred term
Q1	first quartile
Q3	third quartile
SAE	serious adverse event
SAP	statistical analysis plan
SD	standard deviation
SOC	system organ class
SVR	sustained virologic response
SVRx	sustained virologic response x weeks after stopping study drug
TD	target detected
TND	target not detected
ULN	upper limit of normal

STUDY DEFINITIONS

HCV virological suppression is defined as HCV RNA below the lower limit of quantitation (LLOQ) (target not detected [TND] or target detected, not quantifiable [TDnq]).

An *end-of-treatment response (ETR)* is defined as plasma HCV RNA below the LLOQ (TND or TDnq) at the end of treatment.

Sustained virological response at 4 weeks post-treatment (SVR4) is defined as plasma HCV RNA below the LLOQ (TND or TDnq) at 4 weeks post cessation of treatment.

Sustained virological response at 12 weeks post-treatment (SVR12) is defined as plasma HCV RNA below the LLOQ (TND or TDnq) at 12 weeks post cessation of treatment.

Sustained virological response at 24 weeks post-treatment (SVR24) is defined as plasma HCV RNA below the LLOQ (TND or TDnq) at 24 weeks post cessation of treatment.

HCV virologic failure is defined as *non-response* (failure of virological suppression on-treatment with quantifiable HCV RNA at all time points between baseline and end of treatment)

Reinfection is defined by the presence of quantifiable HCV RNA after an ETR and detection of infection with an HCV strain that was distinct from the primary infecting strain (heterologous virus on sequencing of Core-E2 and/or NS5B regions).

Relapse is defined by recurrent viraemia by SVR12 where reinfection is not confirmed.

The *presentation of recent HCV infection* at the time of diagnosis is classified as either *acute clinical* or *asymptomatic infection*. *Acute clinical infection* includes participants with a documented clinical history of symptomatic seroconversion illness (including, but not limited to, the presence of jaundice, nausea/vomiting, abdominal pain, fever and hepatomegaly) and those without clinical symptoms but with a documented peak ALT >10 times the upper limit of normal (ULN) within the 12 months prior to diagnosis. *Asymptomatic infection* includes participants with anti-HCV antibody seroconversion but no acute clinical symptoms or documented peak ALT <10x ULN.

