The modified Intention to Treat (mITT) population includes participants in the FAS excluding those with non-virological reasons for treatment failure (i.e., death, loss to follow up) and reinfection. Participants with confirmed reinfection after achieving an ETR, but prior to the primary efficacy endpoint (SVR12), will be excluded from the mITT.

Per-protocol Analysis Set

The PP population is defined as all participants who received >90% of scheduled treatment for >90% of the scheduled treatment period with follow-up virologic data to SVR12.

Safety Population

The Safety population includes all participants who randomised and will be analysed and presented according to the actual on-treatment monitoring arm received during the study.

The ITT population will be used for primary efficacy analyses, and the safety population will be used for all safety analyses.

Data Handling Conventions

Missing Data

For the analyses of categorical HCV RNA data, missing post-treatment HCV RNA data will have the missing data imputed. Missing on-treatment HCV RNA will have the missing data imputed up to the time of the last dose.

If a data point is missing and is preceded and followed in time by values that are "<LLOQ, TND," then the missing data point will be set to "<LLOQ, TND."

If a data point is missing, and preceded and followed by values that are "<LLOQ, target detected," or preceded by "<LLOQ, target detected" and followed by "<LLOQ, TND," or preceded by "<LLOQ, TND" and followed by "<LLOQ, target detected," then the missing value will be set to "<LLOQ, target detected."

If a data point is missing, and preceded and followed by values that are ">LLOQ, target detected," or preceded by ">LLOQ, detected" and followed by "<LLOQ, target detected" or "<LLOQ, TND", then the missing value will be set to ">LLOQ, target detected."

The following scenarios describe a framework for analysis of the primary endpoint based on various anticipated events for the ITT and mITT population:

- i. In the event of the participant dying or becoming lost to follow-up prior to SVR 12, the participant will be considered to have failed treatment (loss to follow up = failure)
- ii. If the SVR 12 time-point measure is missing, then the next available measure (i.e., SVR 24 or later) will be used. If no future time points are available, the participant will be considered a treatment failure.

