Use of NEW sterile needle and syringe in last month, n (%)			
All injections			
..Most of the time ^a			
Half of the time			
Some of the time			
Not in the last month			
How many times in last month used a needled/syringe after someone else, n (%)			
None			
One time			
Two times			
3 – 5 times			
More than 5 times			
Who did you share with?, n (%)			
No-one			
Regular sex partner			
Casual sex partner			
Close friends			
Acquaintance			
Other			
How many times in last month has someone used a needled/syringe after you, n (%)			
None			
One time			
Two times			
3 – 5 times			
More than 5 times			
Who were these people that shared after you?, n (%)			
No-one			
Regular sex partner			
Casual sex partner			
Close friends			
Acquaintance			
Other			

^a Denominator – those reporting injecting drug use in last month

STUDY ENDPOINTS

Table 12. Study endpoints and outcomes

Primary endpoint	Non-inferiority of simplified on-treatment monitoring to standard on-treatment monitoring (ITT population)	Included in primary analysis	
Secondary endpoints	Non-inferiority of simplified on-treatment monitoring to standard on-treatment monitoring (mITT population)	Included in primary analysis	
	Non-inferiority of simplified on-treatment monitoring to standard on-treatment monitoring (PP population)	Included in primary analysis	
	Treatment response: ETR, SVR4, SVR24; HCV RNA below the level of quantification through 2 years post treatment	Included in primary analysis	
	Adverse events	Included in primary analysis	
	On-treatment adherence	Included in primary analysis	
	Early treatment discontinuation	Included in primary analysis	
	Relapse and reinfection	Included in primary analysis	
	Resistance associated substitutions (RAS) for people who have failed treatment	Included in primary analysis	
	Laboratory abnormalities	Included in primary analysis	
	Change in HIV RNA and CD4 (on treatment and end of treatment)	Included in primary analysis	
			Included in primary analysis
Additional pre-specified outcomes	Factors associated with on treatment efficacy (only if SVR12 is low)	Included in primary analysis	
	Factors associated with sub-optimal adherence		
	Factors associated with re-infection	Not included in primary analysis	
	To evaluate the impact of treatment on illicit drug use, injecting behaviour and sexual risk-taking behaviour (behavioural survey) during treatment	Not included in primary analysis	

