	To evaluate patient interest and attitudes towards long acting parenteral hepatitis C therapy (Long-Acting Hepatitis C Therapy Questionnaire)	Not included in primary analysis	

Primary efficacy endpoint

The proportion of participants with HCV RNA below the level of quantitation (target not detected [TND] or target detected, not quantifiable [TDnq]) at 12 weeks post end of treatment (SVR12)

The primary analysis will compare randomised treatment groups on an ITT basis including all available data. The primary endpoint, SVR12, will be calculated for each patient based on all available data. Treatment arms will be regarded as non-inferior if the difference in proportion between regimens has a lower limit greater than -12%. Secondary analyses will compare randomised treatment groups based on available data (per protocol).

Secondary efficacy endpoints

- Virological endpoints
 - The proportion of treated participants with:
 - ETR (defined as undetectable plasma HCV RNA at the end of treatment)
 - SVR4 (defined as undetectable plasma HCV RNA at post-treatment week 4)

For virological endpoints, the point estimates and 95% exact confidence intervals will be reported by study arm, by HCV genotype and by HIV serostatus.

Virological endpoints (Table 13 and 14)

The presence of HCV RNA will be assessed at all scheduled clinic study visits using Aptima HCV Quant Dx assay, version 2.15.5 (lower limit of quantitation [LLOQ] 10IU/mL; Hologic, Inc., Marlborough, MA, USA), with centralised testing performed at St Vincent's Centre for Applied Medical Research (Sydney, NSW, Australia).

Proportions and 95% confidence intervals will be reported for both the primary and secondary virological endpoints. Virological endpoints will be assessed in the ITT, mITT and PP populations, with results stratified by HCV genotype/subtype and HIV serostatus.

Factors associated with treatment outcome in the ITT population will be evaluated by univariate analysis. Variables assessed will include but are not limited to: demographic factors (age, gender); virological factors (baseline HCV RNA, genotype 1 subtype, duration of HCV infection); risk behaviors (injecting drug use, sexual behavior, mode of HCV acquisition); HIV co-infection; treatment factors (adherence).

Primary safety endpoints

The primary safety endpoints are:

- Proportion of participants with common adverse events (reported by greater than 5% of the study population);

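### The SAP's mITT set has two conflicting reinfection rules, one without a time limit and one that stops at SVR12, and neither suits every endpoint the set is used for

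*SAP*

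**What the plan says.** The SAP, under Modified Full Analysis Set, starts from the full analysis set, "excluding those with non-virological reasons for treatment failure (i.e., death, loss to follow up) and reinfection". No time limit is attached to reinfection there. The next sentence reads: "Participants with confirmed reinfection after achieving an ETR, but prior to the primary efficacy endpoint (SVR12), will be excluded from the mITT". Protocol 11.3 gives the rule without a limit: "Modified intention-to-treat analyses will also be performed in which individuals with confirmed reinfection are removed from the efficacy analysis".

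The set is not reserved for SVR12. Under Virological endpoints the SAP states: "Virological endpoints will be assessed in the ITT, mITT and PP populations". Table 12 lists, among secondary endpoints marked for the primary analysis, "Treatment response: ETR, SVR4, SVR24; HCV RNA below the level of quantification through 2 years post treatment". Table 13 has an SVR24 row, and the text after it says that the tables will be repeated for the mITT and per-protocol populations.

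Two definitions matter. "Sustained virological response at 24 weeks post-treatment (SVR24) is defined as plasma HCV RNA below the LLOQ (TND or TDnq) at 24 weeks post cessation"; it makes no exception for reinfection. "Relapse is defined by recurrent viraemia by SVR12 where reinfection is not confirmed". The SAP's definition of reinfection, by contrast, has no end date: quantifiable RNA after an end-of-treatment response (ETR), with a distinct strain.

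Under Missing Data, for both ITT and mITT, a missing SVR12 result is replaced by the next available one, from SVR24 or later.

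**The concern.** The purpose of removing reinfection is to separate failure of the drug from new exposure. A single fixed set can do this cleanly only if the exclusion is tied to the endpoint being analysed. Here the same set serves endpoints at 4, 12 and 24 weeks and possibly 2 years, while the text leaves open whether the cut-off is SVR12 or absent. Two programmers could build different mITT sets from the same page, and either set gives a poor answer at one endpoint or another. At stake are the mITT SVR24 figure, any 2-year mITT figure and, through the substitution rule, individual results in the mITT SVR12 analysis, which Table 12 lists as a secondary endpoint.

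**Working it through.** The plan gives no figure for this point. The check sets the rules side by side and then illustrates the scale.

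**Reading 1: the SVR12 limit governs.** Take a participant suppressed at SVR12 who acquires a distinct strain before week 24 and is viraemic at that visit.
- The participant stays in the mITT set and, by the SVR24 definition, is not a responder. The per-protocol definition does not remove such a person either.
- Suppose the SVR12 sample was missing. The SAP's three bracketing rules do not cover a suppressed value followed by a quantifiable one, so the next available measure applies. A reinfection acquired after week 12 then becomes an mITT SVR12 failure.
- The post-treatment week 24 window in Table 2 opens at day 147 and has no upper limit, so late samples can be assigned to it.

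**Reading 2: no time limit.** The same participant, a responder at SVR12, is dropped from the SVR12 analysis because of a later event. Taken literally, protocol 11.3 does this too.

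**Scale.** Inputs:
- 192 participants, 99 standard and 93 shortened (SAP, Full Analysis Set).
- 90% response (the planning value for the control arm, assumed here for both arms), so 0.90 × 192 = 172.8 responders.
- Follow-up to post-treatment week 96 (protocol 4.1).
- Reinfection rates from protocol 1.3.6: 4.7 per 100 person-years in the earlier Australian acute hepatitis C cohort, and 7.8 in a cohort of HIV-positive MSM.

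Further assumptions: constant rate, no loss to follow-up, no late relapse, no other mITT exclusions, and SVR12 non-responders kept in the set.

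Proportion reinfected = 1 − exp(−rate × time), with time 12/52 = 0.231 years (weeks 12 to 24) or 84/52 = 1.615 years (weeks 12 to 96). If R people are reinfected, the mITT proportion is (172.8 − R)/192 when they are kept and (172.8 − R)/(192 − R) when they are removed.

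| Rate per 100 py | Interval (weeks) | Reinfected | R | Kept | Removed | Gap (points) |
|---|---|---|---|---|---|---|
| 4.7 | 12–24 | 1.1% | 1.9 | 89.0% | 89.9% | 0.9 |
| 7.8 | 12–24 | 1.8% | 3.1 | 88.4% | 89.8% | 1.4 |
| 4.7 | 12–96 | 7.3% | 12.6 | 83.4% | 89.3% | 5.9 |
| 7.8 | 12–96 | 11.8% | 20.5 | 79.3% | 88.8% | 9.5 |

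For scale, the standard error of a 90% proportion is √(0.9 × 0.1/99) = 3.0 points in the standard arm and √(0.9 × 0.1/93) = 3.1 points in the shortened arm. The 2-year gap is thus roughly 2 to 3 standard errors of one arm's estimate.

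**Sensitivity to the rate.** The same section of the protocol cites 1.8, 2.4 and 2.8 per 100 person-years, the last for late relapse or reinfection combined. At 1.8 and 2.8, 2.9% and 4.4% are affected by week 96 (R = 5.0 and 7.6), and the gap is 2.3 and 3.6 points. The 4.7 rate rests on 5 cases; its interval of 1.9 to 11.2 corresponds to 3.0% to 16.5% reinfected by week 96.

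**The case against.** The strongest reply is that there is no real conflict. The sentence before the time-limited one removes reinfection without a limit and so agrees with the protocol, and the second sentence nowhere says that only early reinfections are excluded. A reader might infer that the SAP has overridden the protocol and counts every late reinfection as treatment failure. The documents do not say so; this follows only if the second sentence governs. What stands is that, if the first sentence already removed all reinfections, the second would add nothing, so the intended rule cannot be settled from the text.

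The second reply is scope. The SAP describes the primary analysis on data through post-treatment week 12. Its bulleted list of secondary efficacy endpoints names only ETR and SVR4, and the 2-year endpoint has neither a row in Table 13 nor an analysis window. Table 12 is imperfect evidence of intent, because it words its primary endpoint as a comparison of monitoring strategies that this trial does not make. This weakens the 2-year part, which carries most of the magnitude. It does not remove the SVR24 part: the SVR24 row is there and is to be repeated for mITT.

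A reader might also infer that failures after SVR12 cannot be divided into relapse and reinfection. That is too strong. The SAP's reinfection definition is open-ended, and protocol 11.3 plans sequencing of recurrences with cut-offs for both. The gap is one of labelling: a same-strain recurrence after SVR12 has no name in the SAP. Nor do the documents say that late reinfection will be presented as lack of drug durability; protocol 2.3 states the 2-year objective simply as a proportion with undetectable RNA.

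**Conclusion.** The mITT reinfection rule is internally inconsistent and should be settled before the set is built. This is more than missing detail, because one fixed set fails under either reading: late reinfections become non-responses at SVR24 and later, or SVR12 responders are dropped for a subsequent event.

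The effect is small at SVR24, about 2 to 3 people in the whole trial. It is larger in any 2-year mITT proportion, at about 6 to 9.5 points, if the rates of 4.7 to 7.8 apply with 90% response, a constant rate and no losses. It is about 2 to 4 points at the lower rates the protocol cites. The SAP records that the short arm was stopped for inferiority, so 90% may be too high there; fewer responders would reduce the gap.

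A reader might carry this over to the main result. The primary ITT SVR12 analysis does not use the mITT rule and is unaffected. No effect on the difference between arms is shown either: with equal reinfection rates, most of the shift would be common to both.

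**What to change.** Under Modified Full Analysis Set, replace the two sentences with one endpoint-specific rule. For each virological endpoint, the mITT set excludes participants whose confirmed reinfection, after an ETR, occurs before the time point being analysed. State that the same exclusion applies when a later value is substituted for a missing SVR12 and that value reflects confirmed reinfection. Add a footnote to the mITT tables that the denominator varies by time point.

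Under Study Definitions, let relapse cover same-strain recurrence at any time after ETR, and keep the SVR12 limit for Table 17 only.

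A cumulative incidence of relapse with reinfection as a competing event would be a useful addition at 2 years but is optional.

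The cost is SAP wording and a footnote. Sequencing of recurrences is already planned, so no new data are needed. The one drawback is an mITT denominator that changes between rows of the same table.
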